#### CONFIDENTIAL AND PROPRIETARY

## Prospective multi-center study comparing REGENETEN in lieu of standard arthroscopic repair of high-grade (>50%) partial-thickness tears

Number: REGEN.PUB.2018.09 Version: 3.0, 10SEP2019 Page: Page 44 of 105

smith&nephew

ltem	Objective	Outcome Measure	Statistical Test	
Secondary Objective #25	To determine if participants who undergo arthroscopic surgical treatment of high-grade (>50%) partial-thickness rotator cuff tears using REGENETEN have statistically improved rotator cuff integrity (based on MRI assessment) compared to participants who had standard surgical repair techniques at 24 months from the index surgery.	ho Sugaya score N/A (based on MRI 6) assessment) at ears 24-months post- surgery.		
Secondary Objective #26	To determine if participants who undergo arthroscopic surgical treatment of high-grade (>50%) partial-thickness rotator cuff tears using REGENETEN have a lower incidence of revision surgeries (index shoulder; all causes) compared to participants who had standard surgical repair over the 24 months from the index shoulder surgery.	Incidence of revision surgery (index shoulder; all cause) within 24m of the index surgery.	Logistic regression analysis adjusting for differences in baseline characteristics.	
Secondary Eco	onomic Objectives/Outcomes			
ltem	Objective	Outcome Measure	Statistical Test	
Secondary Objective #27	To determine if arthroscopic surgical treatment of high-grade (>50%) partial-thickness rotator cuff tears using REGENETEN results in lower aggregate heath care costs over 12 months post- index surgery than standard surgical repair.	Costs based on healthcare resource utilization as listed below.	N/A	
Secondary Objective #28	To determine if arthroscopic surgical treatment of high-grade (>50%) partial-thickness rotator cuff tears using REGENETEN requires less operating room time than standard surgical repair.	Operating room time as measured from time of first incision to wound closure measured in minutes.	Generalized linear regression, adjusting for differences in baseline characteristics.	

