## 9.2.2 Economic Endpoints

Aggregate health care utilization costs: Related health care utilization costs over 12 months postsurgery will be calculated based on health care utilization as reported in the participant diary and/or in the participant's medical records.

*Operating Time (Index surgery):* Operating time for the index surgery, defined as the time from first incision to wound closure (measured in minutes) as recorded in the operative procedure notes, will be recorded.

*Medication Use:* Cumulative opioid and non-opioid prescription medication used to treat the index shoulder over 12 months following index surgery as reported in the participant diary and/or in the participant's medical record, will be recorded.

*Number of Steroid Injections:* The number of steroid injections administered to the index shoulder within 12 months of the index surgery as reported in the participant diary and/or in the participant's medical record, will be recorded.

*Number of Unscheduled Clinic Visits:* The number of unscheduled clinic visits (defined as a return visit to a health care provider for examination/evaluation of the index shoulder) within 12 months of the index surgery, as reported in the participant diary and/or in the participant's medical record, will be recorded.

*Number of For-Cause Imaging Procedures:* The number of for cause imaging procedures (e.g. MRI or ultrasound) performed on the index shoulder within 12 months of the index surgery, as reported in the participant diary and/or in the participant's medical record, will be recorded.

*Number of Physiotherapy Sessions:* The number of physiotherapy sessions within 12 months of the index surgery, as reported in the participant diary and/or in the participant's medical record, will be recorded.

This document contains information that is confidential and proprietary to Smith & Nephew PLC and Smith & Nephew, Inc. and is intended for use only by Smith & Nephew and its manufacturer. It shall not be reproduced or copied in whole or in part, nor shall the contents be disclosed by any means without prior written permission from Smith & Nephew, nor shall anyone make any use of it that is contrary to the expressed or implied wishes of Smith & Nephew.

Study Protocol—Device	Smith&nephew
lieu of standard arthroscopic repair of high-grade (>50%)	REGEN.PUB.2018.09
	Version: 3.0, 10SEP2019 Page: Page 35 of 105

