#### CONFIDENTIAL AND PROPRIETARY

## Prospective multi-center study comparing REGENETEN in lieu of standard arthroscopic repair of high-grade (>50%) partial-thickness tears

 Number:

 REGEN.PUB.2018.09

 Version: 3.0, 10SEP2019

 Page: Page 45 of 105

>smith&nephew

ltem	Objective Outcome Statistica Measure		Statistical Test	
Secondary Objective #29	To determine if participants who undergo arthroscopic surgical treatment of high-grade (>50%) partial-thickness rotator cuff tears using REGENETEN receive fewer shoulder steroid injections compared to standard surgical repair over the 12 months from the index shoulder surgery.Number of steroid injections in the 		N/A	
Secondary Objective #30	To determine if participants who undergo arthroscopic surgical treatment of high-grade (>50%) partial-thickness rotator cuff tears using REGENETEN have fewer index shoulder-related unscheduled clinic visits compared to standard surgical repair over the 12 months from the index shoulder surgery.	Number of index shoulder-related unscheduled clinic visits within 12 months of index surgery.	N/A	
Secondary Objective #31	To determine if participants who undergo arthroscopic surgical treatment of high-grade (>50%) partial-thickness rotator cuff tears using REGENETEN have fewer for-cause imaging procedures compared to standard surgical repair over the 12 months from the index shoulder surgery.	Number of for cause imaging procedures (e.g. MRI, ultrasound) within 12 months of index surgery.	N/A	
Secondary Objective #32	To determine if participants who undergo arthroscopic surgical treatment of high-grade (>50%) partial-thickness rotator cuff tears using REGENETEN undergo less physiotherapy compared to standard surgical repair over the 12 months from the index shoulder surgery.	Number of physiotherapy sessions within the 12 months of the index surgery	N/A	

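### The aggregate cost endpoint (#27) has two definitions that do not match, and neither counts the implant or the comparator's repair materials, so it cannot show lower aggregate health care costs

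*Combined protocol and SAP*

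**What the plan says.** The objective in Table 2 (section 10.4.2, row #27) is to determine whether treatment with REGENETEN results in "lower aggregate heath care costs over 12 months". The outcome measure is "Costs based on healthcare resource utilization as listed below", and the statistical test is given as N/A. Five rows follow:

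- #28: "Operating room time as measured from time of first incision to wound closure measured in minutes".
- #29: steroid injections. The objective is that REGENETEN participants "receive fewer shoulder steroid injections compared to standard surgical repair over the 12 months".
- #30: "Number of index shoulder-related unscheduled clinic visits within 12 months of index surgery".
- #31: "Number of for cause imaging procedures (e.g. MRI, ultrasound) within 12 months of index surgery".
- #32: physiotherapy sessions over the same 12 months.

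Section 9.2.2 defines the endpoint differently: "Related health care utilization costs over 12 months postsurgery will be calculated based on health care utilization as reported in the participant diary". Medical records are named there as a further or alternative source. It gives no closed item list. The same section includes medication among the economic endpoints: "Cumulative opioid and non-opioid prescription medication used to treat the index shoulder over 12 months".

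Section 6.1 describes the REGENETEN system as a collagen implant, anchors and disposable instruments, supplied for single use. Section 8.2 defines the comparator as transtendinous repair after debridement, or takedown and repair. Section 10.1 assigns the economic analysis to the sponsor's own biostatistics group.

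**The concern.** An aggregate cost comparison should include the resource that separates the two strategies. Here that is what is implanted and used up in theatre: the REGENETEN system in one cohort and the repair's own materials in the other. Table 2 counts the minutes of the index operation but not the materials used during them. Section 9.2.2 points to the period after surgery and does not name materials either.

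A finding of lower aggregate cost could therefore be reported when the full cost of the REGENETEN strategy is equal or higher. The two definitions also leave the analyst free to decide whether operating time, medication and revision surgery belong in the sum. Because #27 has no statistical test, the endpoint definition is nearly all of its prespecification. Section 10.6 plans a one-year analysis with a possible peer-reviewed publication, and by then the 12-month cost window is complete.

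**Working it through.** The plan states no cost figure, unit price or expected cost difference, so there is nothing to reproduce. The check sets the two definitions side by side and then works out what an omitted item does to the comparison.

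| Resource | Table 2, rows below #27 | Section 9.2.2 |
|---|---|---|
| Index operating time | Listed (#28) | Separate endpoint; the cost window is after surgery, so inclusion is unclear |
| Injections, unscheduled visits, for-cause imaging, physiotherapy | Listed (#29 to #32) | Covered as related utilization |
| Opioid and non-opioid prescription medication | Not listed | Named as an economic endpoint; not said to enter the sum |
| Revision surgery within 12 months | Not listed (#26 stands above #27 and runs to 24 months) | Not named; could enter through medical records |
| REGENETEN implant, anchors, disposables | Not listed | Not named |
| Comparator's repair materials | Not listed | Not named |
| Unit costs or price source | None | None |

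Two things follow. The definitions differ on operating time, medication and possibly revision. They agree in leaving out index-procedure materials in both cohorts.

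**Effect of the omissions.** Write each difference as REGENETEN minus standard repair, in mean cost per participant. Let ΔM be materials, ΔRx medication and ΔRev revision within 12 months. Then

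full difference = Table 2 difference + ΔM + ΔRx + ΔRev,

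so the shift (Table 2 difference minus full difference) = −(ΔM + ΔRx + ΔRev). A negative shift flatters REGENETEN.

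Set ΔM = +1 unit. Both its sign and its size are assumptions, because the documents price neither cohort's materials. Take ΔRx from −0.5 to +0.5 and ΔRev from −1.0 to +0.5, also assumed:

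- ΔRx = 0, ΔRev = 0: shift = −(1 + 0 + 0) = −1.0.
- ΔRx = +0.5, ΔRev = +0.5: shift = −(1 + 0.5 + 0.5) = −2.0.
- ΔRx = −0.5, ΔRev = −0.5: shift = −(1 − 0.5 − 0.5) = 0.
- ΔRx = −0.5, ΔRev = −1.0: shift = −(1 − 0.5 − 1.0) = +0.5.

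The range is −2.0 to +0.5. The sign turns where savings on medication and revision together equal the extra cost of materials.

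**Under section 9.2.2 read broadly.** If medication and revision are both counted, ΔRx and ΔRev leave the expression and the shift is −ΔM. If operating time is left out as well, it becomes −(ΔM + ΔOT), where ΔOT is the difference in operating-time cost. ΔM remains under either definition.

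**The case against.** Four points can be made for the plan.

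First, the Table 2 cell should not be read as a closed list. Section 9.2.2 is broader, the diary's utilization list in section 9.1.4 is open-ended, and section 9.1.5 has sites record index-shoulder utilization that the diary missed. This stands for medication and for revision within 12 months: both are inconsistently handled, not clearly excluded. It does not help with materials, which neither definition names.

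Second, operating time may sit below #27 only because it is the next endpoint, and the post-surgery window suggests it was not meant to be in the cost. That is a fair reading, but Table 2 taken literally includes it. The conflict is itself part of the point.

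Third, a reader might infer that the comparison favours REGENETEN by construction. The documents do not support that. Only the materials omission points that way, and only if REGENETEN's materials cost more than the comparator's. Section 5.2 expects less medication (objectives 8 to 11) and fewer revisions (objective 26) with REGENETEN, so leaving those out would work against it. That the sponsor's group runs the analysis is openly stated and is not evidence of bias. A dollar estimate of the effect would be equally unsupported.

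Fourth, #27 is one of 32 secondary objectives, is reported descriptively and does not touch the primary endpoint. Section 10 also defers detail to a separate SAP, to be finalized before database lock, which is not in the document reviewed and may settle the list. This limits the consequence. But the rule as written leaves out an item that the objective's own question requires, which goes beyond unspecified detail.

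**Conclusion.** The point holds in this form: #27 has two non-matching definitions, and under both the cost of index-procedure materials is missing in both cohorts. As planned, the sum cannot support a conclusion of lower aggregate health care costs.

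The materials omission shifts the reported difference by exactly the net difference in materials cost, in REGENETEN's favour if its materials are dearer. The direction of the total shift is not fixed: −2.0 to +0.5 per unit of net materials cost under the assumed ranges above. No monetary size can be given. The conclusion rests on the current text of Table 2 and section 9.2.2, and would fall away if the separate SAP sets a closed list that includes materials. It should be corrected before the one-year analysis; the primary comparison is unaffected.

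**What to change.** Reconcile Table 2 and section 9.2.2 into one closed list:

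1. Index procedure, both cohorts: operating time, implant or repair materials, anchors and disposables.
2. Index-shoulder utilization within 12 months: injections, unscheduled visits, for-cause imaging and physiotherapy.
3. Opioid and non-opioid prescription medication within 12 months.
4. Any revision surgery on the index shoulder within 12 months, taken from the data already gathered for #26.

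Apply one unit-cost list to both cohorts, name its source, and fix both lists before the one-year analysis.

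If only downstream cost is wanted, remove index operating time from the sum, label the endpoint as post-operative utilization cost excluding index-procedure and device cost, and drop the aggregate-cost claim from #27.

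The cost is wording in the protocol and SAP plus a unit-price list. Utilization, medication, revision and operating time are already collected. The case report forms are not in the documents, so whether they record materials used should be checked. The downside for the sponsor is that the cost result may look less favourable.

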#### CONFIDENTIAL AND PROPRIETARY

## Prospective multi-center study comparing REGENETEN in lieu of standard arthroscopic repair of high-grade (>50%) partial-thickness tears

 Number:

 REGEN.PUB.2018.09

 Version: 3.0, 10SEP2019

 Page: Page 45 of 105

>smith&nephew

ltem	Objective Outcome Statistica Measure		Statistical Test	
Secondary Objective #29	To determine if participants who undergo arthroscopic surgical treatment of high-grade (>50%) partial-thickness rotator cuff tears using REGENETEN receive fewer shoulder steroid injections compared to standard surgical repair over the 12 months from the index shoulder surgery.Number of steroid injections in the 		N/A	
Secondary Objective #30	To determine if participants who undergo arthroscopic surgical treatment of high-grade (>50%) partial-thickness rotator cuff tears using REGENETEN have fewer index shoulder-related unscheduled clinic visits compared to standard surgical repair over the 12 months from the index shoulder surgery.	Number of index shoulder-related unscheduled clinic visits within 12 months of index surgery.	N/A	
Secondary Objective #31	To determine if participants who undergo arthroscopic surgical treatment of high-grade (>50%) partial-thickness rotator cuff tears using REGENETEN have fewer for-cause imaging procedures compared to standard surgical repair over the 12 months from the index shoulder surgery.	Number of for cause imaging procedures (e.g. MRI, ultrasound) within 12 months of index surgery.	N/A	
Secondary Objective #32	To determine if participants who undergo arthroscopic surgical treatment of high-grade (>50%) partial-thickness rotator cuff tears using REGENETEN undergo less physiotherapy compared to standard surgical repair over the 12 months from the index shoulder surgery.	Number of physiotherapy sessions within the 12 months of the index surgery	N/A	

## 10.4.3 Analysis of Other Endpoint(s)

Not applicable.

This document contains information that is confidential and proprietary to Smith & Nephew PLC and Smith & Nephew, Inc. and is intended for use only by Smith & Nephew and its manufacturer. It shall not be reproduced or copied in whole or in part, nor shall the contents be disclosed by any means without prior written permission from Smith & Nephew, nor shall anyone make any use of it that is contrary to the expressed or implied wishes of Smith & Nephew.

Study Protocol—Device	%smith&nephew
Prospective multi-center study comparing REGENETEN in lieu of standard arthroscopic repair of high-grade (>50%) partial-thickness tears	Number: REGEN.PUB.2018.09 Version: 3.0, 10SEP2019 Page: Page 46 of 105

#### 10.5 SAFETY ANALYSES

Frequency of the treatment-emergent AEs will be calculated for: each body system, by preferred terminology, and overall; by treatment cohort, for the number of participants and percentage of participants reporting the event. The seriousness, severity of the adverse events and the relationship to the investigational product will be summarized for: each body system, preferred terminology, and overall; by treatment group. Serious adverse events (SAE) (including deaths) will be listed for individual events.

The Sponsor will prepare narratives for all deaths, non-fatal serious adverse events, and participants withdrawn due to adverse events

The number and percentage of participants reporting treatment-emergent adverse events split by treatment separately by system organ class, and preferred term will be summarized by:

1. Their relationship with the investigational device (not related or related). If the relationship is missing, the adverse event will be assumed to be treatment-related and a footnote will be added to the table. If a participant experiences more than one preferred term within a system organ class, then the relationship at the system organ class level for that subject will be reported according to their most related relationship for each preferred term.

- 2. The severity of the adverse event (mild, moderate or severe).
- 3. Whether or not the adverse event is serious
- 4. The adverse event outcome.
- 5. Whether or not the adverse event is expected or unexpected.

#### **10.6** INTERIM ANALYSES

A data extract will be completed when the last enrolled participant has completed their threemonth follow-up visit. A report will not accompany this data extract but the findings may be presented as possible podium or conference activity.

This document contains information that is confidential and proprietary to Smith & Nephew PLC and Smith & Nephew, Inc. and is intended for use only by Smith & Nephew and its manufacturer. It shall not be reproduced or copied in whole or in part, nor shall the contents be disclosed by any means without prior written permission from Smith & Nephew, nor shall anyone make any use of it that is contrary to the expressed or implied wishes of Smith & Nephew.

Study Protocol—Device	Smith&nephew
Prospective multi-center study comparing REGENETEN in lieu of standard arthroscopic repair of high-grade (>50%) partial-thickness tears	Number: REGEN.PUB.2018.09
	Version: 3.0, 10SEP2019 Page: Page 47 of 105

An interim analysis will be conducted when the last enrolled participant has completed their oneyear follow-up from index surgery. This analysis will include a simplified statistical report and a possible peer-reviewed publication. Further details will be provided in the SAP.

## 11. SAMPLE SIZE JUSTIFICATION

The sample size calculation was conducted for 80% power and an alpha of 0.05. The minimal clinically important difference (MCID) used as the difference to detect for was 11.1 points on the American Shoulder and Elbow Surgeons (ASES) score at 3 months following index surgery. An effect size of 0.56 was used to ensure that the difference in results represented a moderate difference in effect, as defined by Cohen's d. The sample size calculations were completed in R statistical software (v3.5.0). Based on the calculation conducted, a sample size of 102 (51 per arm) was determined. To account for a dropout rate of 15%, the sample size was increased to 118 (59 per arm).

## 12. ADVERSE EVENTS AND DEVICE DEFICIENCIES

#### 12.1 **DEFINITIONS**

The categories of adverse events are shown in Table 3. The definitions for each of these categories are given in the subsequent sections.

	NOT DEVICE- RELATED	DEVICE- OR PROCEDURE-RELATED
NON- SERIOUS	Adverse Event (AE)	Adverse Device Effect (ADE)
SERIOUS	SERIOUS ADVERSE EVENT	SERIOUS ADVERSE DEVICE EFFECT (SADE) (SEE 12.1.3)

#### Table 3: Categories of Adverse Event

#### CONFIDENTIAL AND PROPRIETARY

Study Protocol—Device	Smith&nephew
Prospective multi center study comparing PECENETEN in	Number:
neu of standard arthroscopic repair of high-grade (>50%)	REGEN.PUB.2018.09
	Version: 3.0, 10SEP2019
	Page: Page 48 of 105

(SAE)	ANTICIPATED	UNANTICIPATED
	ANTICIPATED SERIOUS	UNANTICIPATED SERIOUS
	Adverse Device Effect	Adverse Device Effect
	(ASADE)	(USADE)

#### 12.1.1 Adverse Event

An Adverse Event (AE) is any untoward medical occurrence, unintended disease of untoward clinical sign (including abnormal laboratory findings) in participants, users or other persons, whether or not causally related to the IP/Ancillary Product.

Note 1: This definition includes events related to the IP, comparator or ancillary products.

Note 2: This definition includes events related to the procedures involved.

Note 3: For users or other persons, this definition is restricted to events related to the IP.

AE is used both to refer to AE which do not meet the definitions of Adverse Device Effects or Serious Adverse Events and as an umbrella term referring to adverse events of all classifications. An AE can be any unfavorable and unintended sign (for example, an abnormal laboratory finding), symptom, or disease. For reporting purposes, emphasis is placed first and foremost on whether or not the event constitutes an untoward medical occurrence.

#### 12.1.2 Adverse Device Effect

An Adverse Device Effect (ADE) is an adverse event that, in the opinion of the investigator, is related to the use of the IP.

Note 1: This definition includes adverse events resulting from insufficient or inadequate instructions for use, deployment, implantation, installation or operation, or any malfunction of the investigational medical device.

This document contains information that is confidential and proprietary to Smith & Nephew PLC and Smith & Nephew, Inc. and is intended for use only by Smith & Nephew and its manufacturer. It shall not be reproduced or copied in whole or in part, nor shall the contents be disclosed by any means without prior written permission from Smith & Nephew, nor shall anyone make any use of it that is contrary to the expressed or implied wishes of Smith & Nephew.

Study Protocol—Device	smith&nephew
lieu of standard arthroscopic repair of high-grade (>50%)	Number: REGEN.PUB.2018.09
	Version: 3.0, 10SEP2019 Page: Page 49 of 105

Note 2: This definition includes any event resulting from use error or from intentional misuse of the investigational medical device.

- **Not Related** An AE is considered to be not related to the use of an IP or the procedure when the effect is DEFINITELY UNRELATED or UNLIKELY to have any relationship to the use of the IP or the procedure;
- Related An AE is considered to be related to the use of an IP or the procedure when there is a POSSIBLE, PROBABLE, or DEFINITE relationship between the AE and the use of the IP or the procedure.

An ADE is further categorized depending on whether the criteria in section 12.1.3 and 12.1.4 are met.

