## 12.1.4 Anticipated/Unanticipated Serious Adverse Device Effect

An Unanticipated Serious Adverse Device Effect (USADE) is a serious ADE which by its nature, incidence, severity or outcome has not been identified in the current version of the risk analysis report.

Note: Anticipated serious adverse device effect (ASADE) is an effect which by its nature, incidence, severity or outcome has been identified in the risk analysis report. There are no ASADE in this study.

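### Adverse device effect is IP-only in its definition but IP-or-procedure in Table 3 and the relatedness scale, so the device-related rows in Section 10.5 depend on which rule is read

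*Combined protocol and SAP*

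**What the plan says.** Five places bear on whether an event counts as device-related.

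- **Section 12.1.2, definition.** An ADE "is an adverse event that, in the opinion of the investigator, is related to the use of the IP". The procedure is not mentioned.
- **Section 12.1, Table 3.** ADE and its serious form (SADE) sit under the column "DEVICE- OR PROCEDURE-RELATED". The opposite column covers only events that are not device-related.
- **Section 12.1.2, relatedness scale.** "An AE is considered to be related to the use of an IP or the procedure when there is a POSSIBLE, PROBABLE, or DEFINITE relationship". The Not Related bullet merges implant and procedure in the same way.
- **Section 10.5.** The tables give "The number and percentage of participants reporting treatment-emergent adverse events split by treatment separately by system organ class, and preferred term". The first summary variable is "Their relationship with the investigational device (not related or related"). If the relationship is missing, "the adverse event will be assumed to be treatment-related".
- **Section 12.1.4.** "There are no ASADE in this study". Any serious device effect is therefore unanticipated (a USADE).

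Two further sections matter. Section 12.3 asks the investigator to assess each event against both device and procedure, where applicable. It does not say whether these are separate entries or which one feeds Section 10.5. Section 10.2 describes the safety analyses as including participants who received the IP.

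**The concern.** Every participant has surgery, but only one cohort receives the implant. Complications of shoulder arthroscopy can occur in both. The rule that separates a procedural complication from a device effect therefore decides what the related rows show and what any comparison of them between cohorts means.

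The scale given to investigators measures relationship to implant or procedure, while the table label says device. If the scale feeds the table, ordinary surgical complications appear as device-related, including in participants with no device. If a separate device assessment feeds it, they do not.

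The label also affects data capture. Section 12.3 sets a reporting timescale for ADEs but lists none for other non-serious events, and Section 9.1.7 records concomitant medication for SAEs and ADEs. Two sites reading different rules could report the same non-serious procedural event differently.

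**Working it through.** No figure in the plan is at issue, so there is none to reproduce. The check sets the rules side by side and then sizes the gap with assumed rates.

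**Step 1. Classify three events under each rule.**

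| Event | Section 12.1.2 definition | Table 3 | Section 10.5 device row |
|---|---|---|---|
| Procedural only, non-serious, REGENETEN | AE | ADE, though it also fits the not-device-related column | Not related if a device assessment feeds it; related if the merged scale does |
| Procedural only, serious, REGENETEN | SAE | SADE, and hence USADE because no anticipated effects exist | As above |
| Procedural only, standard repair | AE or SAE | ADE or SADE | As above, although no device was used |

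The scale in Section 12.1.2 calls all three events related. Section 12.1.1 lists IP, comparator and ancillary products separately, so the comparator cannot be read as the IP.

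**Step 2. Follow the standard-repair cohort.** Under the IP-only rule no event can be device-related, so the count is zero by construction. The exception is a missing relationship, which Section 10.5 counts as related. Under the merged rule the count is an interpretable number of procedure-related events, labelled as device-related.

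**Step 3. Size the gap.** If k participants have only procedure-related events, the merged rule counts k and the IP-only rule counts 0. That is an identity, not an estimate. To give a scale, take 59 participants per cohort (Section 11), an assumed device-related rate pd of 0 to 5% and an assumed procedure-related rate pp of 5% to 20%, treated as independent. The documents give neither rate.

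- IP-only, REGENETEN: 59 × pd, from 59 × 0 = 0 to 59 × 0.05 = 3.0.
- Merged, REGENETEN: 59 × [1 − (1 − pd)(1 − pp)], from 59 × (1 − 1 × 0.95) = 3.0 to 59 × (1 − 0.95 × 0.80) = 14.2.
- IP-only, standard repair: 0, apart from imputed missing values.
- Merged, standard repair: 59 × pp, from 59 × 0.05 = 3.0 to 59 × 0.20 = 11.8.

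**Step 4. Check who is in the table.** Section 10.5 splits its tables by treatment, which needs both cohorts. Section 10.2, read literally as defining the safety set, leaves out standard repair. The two cannot both hold.

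**The case against.** The best defence is precedence. The text before Table 3 says that the definitions follow in later sections, so Table 3 is an overview and Section 12.1.2 governs. The Related and Not Related bullets are a causality scale, not a second definition of an ADE. Section 12.3 already asks about device and procedure. If the CRF holds the two separately, the device table follows directly and agrees with the IP-only definition. Section 10 calls itself a brief description with detail to come in a SAP, and Figures 3 and 4, cited in Section 12.3 for the reporting flow, could not be read here.

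Part of this stands. Precedence settles the Table 3 heading. It does not settle the merged scale, which sits inside Section 12.1.2 itself, nor the device label and the treatment-related imputation in Section 10.5. Section 12.3 does not say which assessment feeds the table. The IP-only definition also takes in events from inadequate implantation instructions, malfunction or use error, which narrows the gap in the REGENETEN cohort but does nothing for standard repair.

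A reader might infer more than the documents support:

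- **That the standard-repair count is meaningless.** It is a structural zero or a mislabelled procedure count, and both can be interpreted once the rule is known.
- **That procedural events there are lost as unrelated.** Section 10.5 tabulates all treatment-emergent events, and their seriousness, severity and outcome, whatever the relationship.
- **That only one relatedness field is collected.** The CRF is not shown.
- **That ADE, SADE or USADE tables are corrupted.** Section 10.5 lists no such tables; the classes act through the definitions and reporting labels.
- **That serious events would be reported late.** SAE and SADE share the 24-hour timescale in Section 12.3.

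**Conclusion.** The conflict is real and should be corrected. It concerns the relatedness classification: whether a purely procedural event is a device effect, whether a serious one is a USADE, and what the device-related rows mean in each cohort. Under the assumed rates, the standard-repair row moves between 0 and 3.0 to 11.8 participants of 59, and the REGENETEN row ranges from 0 to 3.0 under one rule and from 3.0 to 14.2 under the other. Those ranges rest wholly on the assumed rates; the dependence on the rule does not. Under neither rule is the device-related contrast between cohorts a fair safety comparison.

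The separate conflict between Sections 10.2 and 10.5 over whether standard repair belongs in the safety analyses needs settling at the same time. The conclusion assumes that the reporting figures and the CRF do not already resolve the rule. Nothing here touches the primary ASES analysis, the sample size or the tables that ignore relationship.

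**What to change.** 1. Keep the IP-only ADE definition in Section 12.1.2, and align the Table 3 columns and the relatedness scale with it, so that SADE and USADE follow from the device relationship alone.
2. Record relationship to device and relationship to procedure as two entries for every event, as Section 12.3 already implies, and confirm that the CRF has both.
3. In Section 10.5, tabulate all events and procedure-related events for both cohorts, and device-related events for REGENETEN only.
4. Apply the missing-is-related rule to each entry separately, naming the relationship imputed, with no device imputation in standard repair.
5. Reword Section 10.2 so that the safety analyses cover both cohorts as treated, in agreement with Section 10.5.

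The cost is definition wording, a CRF check and one extra table. If the CRF lacks two entries, events already recorded would need reassessment; Appendix 21.1 reports 27 participants treated at the time of amendment 3.0, so an early check is cheaper.
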